1.2 STUDY SCHEMA

Figure 1 Study Schema

BID=twice a day; DBT=double-blind trial; FEN = fenebrutinib; OLE=open-label extension; PO = by mouth; SFU=safety follow-up.

^a An optional OLE to provide open-label fenebrutinib will be available to all eligible participants who complete the DBT phase on study treatment.

^b Participants who complete the DBT phase on study treatment and do not wish to participate in the OLE and participants who have discontinued treatment will have a post-DBT SFU visit.

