Visit	Baseline ^a	Open-Label Extension Phase												UV ^c	Early D/C Visit ^d	SFU	
		1	2	3	4	5	6	7	8	9	10	11, 13, 15, etc.	12, 14, 16, etc.			+4 weeks ^e	
Study week	0	2	4	6 ^b	8	10 ^b	12	14 ^b	16 ^b	20 ^b	24	36+ every 24 weeks thereafter	48 + every 24 weeks thereafter				
Window in Days		±2						±5							±5	±5	
Informed consent	x																
Review of eligibility criteria	x																
Review of contraception methods	x						x				x		x	x	x	x	x
C-SSRS	x						x				x		x		x	x	x
Vital signs ^f	x						x				x		x	x	x	x	x
Complete physical examination ^g	x						x				x		x	(x)	x	x	x
Query for potential unreported relapses	x						x				x			(x)	x		
EDSS ^h	x						x				x		x	(x)	x		
12-lead ECG ⁱ	x		x				x						x		x		

Table 2 Schedule of Activities: Open-Label Extension Phase (cont.)

Visit	Baseline ^a	Open-Label Extension Phase												UV ^c	Early D/C Visit ^d	SFU
		1	2	3	4	5	6	7	8	9	10	11, 13, 15, etc.	12, 14, 16, etc.			+4 weeks ^e
Study week	0	2	4	6 ^b	8	10 ^b	12	14 ^b	16 ^b	20 ^b	24	36+ every 24 weeks thereafter	48 + every 24 weeks thereafter			
Window in Days		±2						±5							±5	±5
Blood tests ^j																
Hematology and full chemistry panel	x						x				x	x	x	(x)	x	x
Limited chemistry panel: ALT, AST, total and direct bilirubin testing		x	x	x	x	x		x	x	x						
Hepatic synthetic function testing (PT, INR, aPTT)							x				x					
Total Ig, IgG, IgA, IgM	x		x		x		x				x	x	x		x	x
Hepatitis B virus DNA ^k	(x)						(x)				(x)		(x)			
Plasma PK sample ^l	x						x				x		x	(x) ^m	x	
Serum and plasma biomarkers ⁿ	x						x				x		[x]		x	x

Table 2 Schedule of Activities: Open-Label Extension Phase (cont.)

Visit	Baseline ^a	Open-Label Extension Phase												UV ^c	Early D/C Visit ^d	SFU
		1	2	3	4	5	6	7	8	9	10	11, 13, 15, etc.	12, 14, 16, etc.			+4 weeks ^e
Study week	0	2	4	6 ^b	8	10 ^b	12	14 ^b	16 ^b	20 ^b	24	36+ every 24 weeks thereafter	48 + every 24 weeks thereafter			
Window in Days		±2						±5							±5	±5
Flow cytometry ^o											x		[x]		x	
Lipids											x		[x]		x	
At home pregnancy test		Monthly testing														
Urine tests																
In clinic pregnancy test ^p	x						x				x		x	(x)	x	x
Urinalysis	x		x				x				x		x	(x)	x	x
MRI ^q	x												[x]	(x)	(x)	
Concomitant medications	x						x				x	x	x	x	x	x
Adverse events	x						x				x	x	x	x	x	x
Study treatment dispensation	x						x				x	x	x			
Study treatment compliance	x						x				x	x	x		x	
RBR RNA, serum and plasma samples (optional) ^r	x						x				x		[x]		x	x

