Telephone interviews ^s		Every 6 weeks (±3 days)														

Table 2 Schedule of Activities: Open-Label Extension Phase (cont.)

C-SSRS = Columbia-Suicide Severity Rating Scale; D/C = discontinuation; eCRF = electronic Case Report Form; EDSS = Expanded Disability Status Scale; HBV = hepatitis B virus; Ig = immunoglobulin; MRI = magnetic resonance imaging; OLE = open-label extension; PK=pharmacokinetic; SFU=safety follow-up; UV= unscheduled visit; x =required, (x) =not always required; [x] = assessment will be carried out every 48 weeks after week 48.

- ^a The baseline visit in the OLE is the same as the Week 12 visit in the DBT phase. Activities performed at the final visit of the randomized controlled period do not need to be repeated.
- ^b *It is preferred that the blood tests performed at these visits are analyzed by the central laboratory during a clinic visit. However, if these are performed by an accredited local laboratory, the results and reference ranges must be added to the appropriate adverse event eCRF when applicable. When treatment codes become available, patients who received fenebrutinib during the DBT phase do not need to perform these visits.*
- ^c UV may be performed, as clinically appropriate. It must be performed in the following situations: 1) if the patient is experiencing neurological worsening, 2) if the patient has $> 3 \times$ ULN AST or ALT, or 3) if the patient is experiencing symptoms that could be associated with worsening liver function. Assessments at UVs may be performed as clinically indicated. In the case of abnormalities in transamine levels or clinical indications of worsening liver function, additional lab testing may be required per medical monitor guidelines (see Table A6-1).
- ^d Participants who discontinue from the study prior to completion should be encouraged to return to the clinic for an Early D/C visit.
- ^e A SFU visit should be performed 4 weeks after early discontinuation of study drug.
- ^f Includes respiratory rate, pulse rate, and systolic and diastolic blood pressure while the participant is in a seated position, and temperature. Temperature should be noted in the participant's notes only.

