7. DISCONTINUATION OF STUDY TREATMENT AND PARTICIPANT DISCONTINUATION OR WITHDRAWAL

7.1 DISCONTINUATION OF STUDY TREATMENT

It may be necessary for a participant to permanently discontinue (definitive discontinuation) study treatment. If study treatment is definitively discontinued, the participant should move to the Safety Follow-up Period. Refer to the schedule of activities (see Section 1.3) for data to be collected at the time of discontinuation of study treatment (“Early Discontinuation Visit”) and the further follow-up evaluations that need to be completed in the Safety Follow-up Period.

Participants must permanently discontinue study treatment if they experience any of the following:

- Any medical condition that the investigator or Sponsor determines may jeopardize the participant's safety if he or she continues to receive study treatment
- Investigator or Sponsor determination that treatment discontinuation is in the best interest of the participant
- Demonstrate active hepatitis B infection
- PML
- First observation of AST or ALT elevation $> 8 \times$ ULN
- AST or ALT elevation $> 5 \times$ ULN persisting more than 2 weeks
- AST or ALT elevation $> 3 \times$ ULN in combination with any of the following:
 - Total bilirubin $> 2 \times$ ULN or clinical jaundice as defined by Hy’s Law
 - INR > 1.5
 - Symptoms of hepatitis, such as fatigue, nausea, vomiting, right upper quadrant pain or tenderness
 - Signs or symptoms of immune-related hepatotoxicity (fever, rash, or eosinophilia $> 5\%$)
- *ALT or AST elevation between $3\text{--}5 \times$ ULN (inclusive) persisting for 4 weeks and in absence of alternative etiology*
- Grade 3 neutropenia (ANC $500\text{--}1000/\text{mm}^3$) persisting more than 1 month or reoccurring
- Grade 4 neutropenia (ANC $< 500/\text{mm}^3$)
- Grade 2 thrombocytopenia (platelet count $50,000\text{--}75,000/\text{mm}^3$) persisting more than one month or reoccurring
- Grade 3 thrombocytopenia (platelet count $25,000\text{--}50,000/\text{mm}^3$) or Grade 4 thrombocytopenia ($< 25,000/\text{mm}^3$)
- Malignancy (with the exception of non-serious local and resectable basal or squamous cell carcinoma of the skin)

- Pregnancy

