Cytopenias have been observed in the ongoing Phase I study of fenebrutinib in oncology participants (Study GO29089) and in the completed Phase II studies of fenebrutinib in participants with rheumatoid arthritis (RA) (Studies GA29350 and GA30067) and systemic lupus erythematosus (SLE) (Studies GA30044 and GA30066). The cytopenias have been monitorable and clinically manageable, although some participants with SLE, enrolled in studies with fenebrutinib, have had protocol-mandated discontinuations because of cytopenias. Participants should be monitored regularly with hematology laboratory evaluations, as outlined in the schedules of activities (see Section 1.3), and should receive appropriate supportive care as clinically indicated. Participants should be advised to seek immediate medical attention if they develop signs and symptoms suggestive of cytopenias (e.g., persistent fever, bruising, bleeding, pallor). Cytopenias should be managed according to local clinical guidelines.

Guidelines for managing study treatment in the event that cytopenia is observed are provided in Table A6-1. Refer to the Fenebrutinib Investigator's Brochure for further details.

A6–1.7 GASTROINTESTINAL EFFECTS

Reversible body weight gain and food consumption changes have been observed in animals. Mild diarrhea, nausea, and abdominal pain have been reported in participants with B-cell malignancies; however, the events have resolved and have not led to study treatment discontinuation. Healthy participants in the multiple-ascending dose Study GA29347 reported events of mild self-limited nausea. Across studies with immune indications receiving blinded or open-label treatment, approximately 5% of enrolled participants have reported nausea, vomiting, diarrhea, or other GI symptoms; these events occurred with similar frequencies in the fenebrutinib and placebo arms.

Throughout the study, participants will be monitored for GI adverse events. Symptomatic treatment according to the investigator's clinical judgment should be provided. Refer to the Fenebrutinib Investigator's Brochure for further details.

A6–1.8 CARDIOVASCULAR EFFECTS

Fenebrutinib is considered to have a low potential to cause QT interval prolongation or to directly affect other cardiovascular parameters in humans at therapeutic exposures.

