Appendix 6: Safety Plan: Management of Identified and Potential Risks

Table A6-1 Guidelines for Management of Participants Who Experience Adverse Events

Event	Action to Be Taken
Infection^a	
Serious Infection	
 • Withhold study drug during antimicrobial//antiviral treatment. • Study drug may resume following full clinical resolution and re-assessment of benefit-risk for the treated patient.
Bleeding events	
Grade 1 or 2	
 • Maintain study drug dosing.
Grade ≥ 3	
 • For Grade ≥ 3 bleeding events, withhold study drug and initiate emergency therapy according to institutional guidelines. 
Study drug may be resumed after the event resolves.

Neutropenia^b	
Grade 1 (ANC < LLN–1500/mm ³) or 2 (ANC < 1500–1000/mm/mm ³)	
 • Maintain study drug dosing.
Grade 3: ANC < 1000–500/mm ³	
 • For the first event, hold study drug and recheck CBC in 7 days. • If neutrophil count has recovered to Grade 1 (> 1500/mm³) or has returned to the normal range, study drug can be resumed. • Discontinue study drug if event persists more than one month or event reoccurs.
Grade 4: ANC < 500 mm ³	
 • Discontinue study drug.
Thrombocytopenia^c	
Grade 1: PLT < LLN–75,000/mm ³	
 • In the absence of bleeding event(s), maintain study drug dosing.
Grade 2: PLT < 75,000–50,000/mm ³	
 • For the first event, hold study drug and recheck CBC in 7 days. • If platelet count has recovered to Grade 1 or has returned to the normal range, study drug can be resumed. • Discontinue study drug if event persists more than one month or event reoccurs.
Grade ≥ 3: PLT < 50,000/mm ³	
 • Discontinue study drug.
Malignancy	
Any malignancy	
 • Discontinue study drug with the exception of non-serious local and resectable basal or squamous cell carcinoma of the skin.

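### Former placebo participants who start fenebrutinib in the OLE have one scheduled blood count in their first 12 weeks on drug, against three for those randomised to it; a low-severity, cheap improvement

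*Protocol*

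**What the plan says.** Table 1 (Section 1.3) schedules hematology with full chemistry at screening and at Weeks 0, 4, 8 and 12 of double-blind treatment. In Table 2 the row "Hematology and full chemistry panel" is marked at OLE baseline and at Weeks 12, 24, 36 and 48 onward. OLE Weeks 2, 4, 6, 8 and 10 carry the limited liver panel, with immunoglobulins added at Weeks 4 and 8.

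Footnote a of Table 2 states: "The baseline visit in the OLE is the same as the Week 12 visit in the DBT phase". Footnote b, attached to Weeks 6, 10, 14, 16 and 20, says that once treatment codes are available "patients who received fenebrutinib during the DBT phase do not need to perform these visits". On entry, Section 1.2 says: "An optional OLE to provide open-label fenebrutinib will be available to all eligible participants who complete the DBT phase on study treatment".

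Section 7.1 requires permanent discontinuation for Grade 3 neutropenia "persisting more than 1 month or reoccurring", with a parallel rule for Grade 2 thrombocytopenia. Grade 4 neutropenia and Grade 3 or 4 thrombocytopenia require it outright. For Grade 3 neutropenia and Grade 2 thrombocytopenia, Table A6-1 adds: "For the first event, hold study drug and recheck CBC in 7 days". On surveillance, Section A6-1.6 says: "Participants should be monitored regularly with hematology laboratory evaluations, as outlined in the schedules of activities". The same section calls cytopenias detectable by monitoring and manageable, but also reports that "some participants with SLE, enrolled in studies with fenebrutinib, have had protocol-mandated discontinuations because of cytopenias".

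**The concern.** For a former placebo participant, the OLE is the first exposure to fenebrutinib. The hold and stop rules can act only on a count that has been taken, and A6-1.6 relies on the schedules to supply those counts. On first exposure in the double-blind phase the sponsor counts every four weeks. On first exposure in the OLE the first scheduled count comes at twelve weeks.

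What is at stake is a silent cytopenia: one that reaches a hold or stop threshold without symptoms and without ALT or AST above 3 × ULN. Scheduled testing could miss it for up to 84 days rather than 28 while dosing continues. This is a participant-safety matter. It does not touch the double-blind comparison or any analysis planned in the SAP.

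**Working it through.** **Inputs.** Hematology rows and visit weeks: protocol Section 1.3, Tables 1 and 2. Timing of OLE baseline: Table 2, footnote a. Arm sizes and 3% dropout: protocol Section 9.2 and SAP Section 3.

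**Arm sizes.** 102 × 2/3 = 68 fenebrutinib and 102 × 1/3 = 34 placebo, which reproduces the stated figures.

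**Participants affected.** The ceiling is the whole placebo arm, 34. With the planning dropout, 34 × (1 − 0.03) = 32.98, about 33. Optional entry can only lower this.

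**Scheduled counts after the first fenebrutinib dose, up to Week 12.**

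| | Randomised to fenebrutinib | Former placebo, in OLE |
|---|---|---|
| On-drug counts | Weeks 4, 8, 12 (three) | Week 12 (one) |
| First on-drug count | 4 × 7 = day 28 | 12 × 7 = day 84 |
| Longest interval, nominal | 28 days | 84 days |
| Longest interval with ±2-day windows | 28 + 2 + 2 = 32 days | 84 + 2 = 86 days |

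The pre-dose count is left out on both sides. The 86-day figure reads Table 2's ±2-day window as covering Weeks 2 to 12. All the intervals are worst cases, with onset just after a count or just after the first dose.

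**Is the blank real?** In both tables the limited liver panel is marked only at weeks where the full panel is not: double-blind Weeks 2, 6 and 10; OLE Weeks 2, 4, 6, 8, 10, 14, 16 and 20. That pattern makes a misread table unlikely.

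**Against the stop rule.** 84 / 28 = 3, so the OLE interval is three times the double-blind one. Grade 3 neutropenia beginning early in the OLE could already have lasted more than a month when the first scheduled count is drawn.

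**Extra counts if Weeks 4 and 8 are added for everyone.** Former placebo 2 × 34 = 68; former fenebrutinib 2 × 68 = 136; total 204, of which 136 / 204 = 67% fall on former fenebrutinib participants. After 3% dropout (33 and 66 participants): 66 + 132 = 198.

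**The case against.** The best defence is that the schedule is proportionate to known risk. Section A6-1.1 reports Grade 2 or higher transaminase elevations in 1% to 10% of participants at 200 mg BID, against fewer than 1% on placebo, and the amendment ties OLE hepatic synthetic function testing to that risk period. For cytopenias, A6-1.6 gives no rate, no placebo comparison and no onset window. The SLE discontinuations arose under other protocols whose thresholds and timing are not given. Section 2.3 reports more than 650 participants on this dose with a consistent safety profile. The double-blind counts also serve a comparative endpoint (SAP Section 5.4.2) that the OLE lacks.

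Most of this stands. A reader might infer from footnote b, which keeps the extra liver visits for former placebo participants once codes are known, that leaving out blood counts was an oversight. The documents do not support that, because the evidence for the two risks differs. A reader might also infer that the protocol breaks its own requirement for regular counts. It does not: A6-1.6 defers to the schedules, and no minimum frequency is set.

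Other routes to a count exist:

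- participants are told to seek care for fever, bruising, bleeding or pallor (A6-1.6);
- all are monitored for fever and infection (A6-1.2);
- six-weekly calls ask about infection (Appendix 10), though none is made when it overlaps a site visit;
- investigators may add tests at any time (Appendix 2), and OLE visits or blood tests fall every two weeks to Week 12;
- a blood count follows ALT or AST above 3 × ULN (Table A6-1);
- Section 8 asks in general terms for a toxicity assessment before each dose;
- low counts are excluded at entry (Section 5.2).

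These make the residual group small. None of them schedules a count that would find a silent cytopenia in the first 84 days, so the gap remains.

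**Conclusion.** The point holds as a low-severity, optional safety improvement. Up to about 34 former placebo participants have one scheduled on-drug count in their first 12 weeks instead of three, under the same hold and stop rules. The longest unscheduled stretch is 84 days against 28, as a worst case.

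Whether twelve weeks is too long cannot be settled from these documents. They give no cytopenia rate for this dose in MS and no onset distribution, so neither the number who would benefit nor an average delay to detection can be stated. The number is likely small. A reader might infer that participants face a demonstrated haematological hazard without monitoring; the documents show neither an estimable harm nor an absence of monitoring. The case rests on consistency with the sponsor's own four-weekly practice at first exposure and on the low cost of matching it.

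**What to change.** Add hematology (CBC with differential and platelets) to Table 2 at OLE Weeks 4 and 8, using the draws already scheduled for the limited liver panel and immunoglobulins. Former placebo participants would then have three scheduled counts in their first 12 weeks on drug, with a longest nominal interval of 28 days. Add a new footnote exempting former fenebrutinib participants from these two counts once treatment codes are available. Footnote b cannot serve, because it is not attached to Weeks 4 or 8. Put the change in the next protocol amendment.

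No visit is added. The cost is up to about 204 central-laboratory counts, about two-thirds of them on already-monitored former fenebrutinib participants if codes are not yet released, plus the usual IRB/EC and health-authority approval (Section A1-1). OLE Week 8 falls 12 + 8 = 20 weeks after randomisation. Participants past that visit when the amendment takes effect gain nothing and cost nothing, so delay shrinks both sides.

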1.3 SCHEDULE OF ACTIVITIES AND SAMPLE COLLECTION SCHEDULE

Table 1 Schedule of Activities

Visit	SCR ^a	Double-Blind Treatment							UV ^c	Early D/C Visit ^d	Safety Follow-Up Visit ^e
	1	2	3	4	5	6	7	8			16 (or 4 weeks after Early D/C)
Study week		0	2 ^b	4	6 ^b	8	10 ^b	12			
Window in Days	-28 to -1	NA	±2	±2	±2	±2	±2	±2	NA	NA	±2
Informed consent ^f	x										
Review of eligibility criteria	x	x									
Randomization		x									
Demographic data	x										
Medical history and baseline conditions	x										
Review of contraception methods	x	x		x		x		x	x	x	x
C-SSRS	x			x		x		x	x	x	x
Vital signs ^g	x	x		x		x		x	x	x	x
Weight		x						x		x	x
Height		x									
Complete physical examination ^h	x	x						x	(x)	x	
Neurological examination ⁱ	x	x						x	(x)	x	
Query for potential unreported relapses		x		x		x		x	x	x	x
EDSS ^j	x	x						x	(x)	x	
12-lead ECG ^k	x	x		x				x		x	
Blood tests: ^l											
Hematology and full chemistry panel	x	x		x		x		x	(x)	x	x

Table 1 Schedule of Activities (cont.)

Visit	SCR ^a	Double-Blind Treatment							UV ^c	Early D/C Visit ^d	Safety Follow-Up Visit ^e
	1	2	3	4	5	6	7	8			16 (or 4 weeks after Early D/C)
Study week		0	2 ^b	4	6 ^b	8	10 ^b	12			
Window in Days	-28 to -1	NA	±2	±2	±2	±2	±2	±2	NA	NA	±2
Limited chemistry panel: ALT, AST, total and direct bilirubin testing			x		x		x				
Hepatic synthetic function testing (PT, INR, aPTT)	x							x	(x)		
Lipids		x						x		x	
Flow cytometry ^m	x	x ⁿ		x		x		x		x	x
Total Ig, IgG, IgA, IgM	x			x		x		x		x	x
Hepatitis B screening ^o	x										
Hepatitis B virus DNA	x			(x)				(x)		(x)	
Hepatitis C screening ^p	x										
HIV screening	x										
Tuberculosis Test (QuantiFERON®-TB Gold)	x										
Plasma PK sample ^q		x		x		x		x	(x)	x	
Additional intensive PK sampling (optional) ^q		x		x							
Serum and plasma biomarkers ^r	x	x ⁿ		x		x		x		x	x
RNA collection (PAXgene tube)	x	x ⁿ						x		x	x
In clinic pregnancy test ^s	x	x		x		x		x	(x)	x	x
Urinalysis		x		x				x	(x)	x	x

Table 1 Schedule of Activities (cont.)

	SCR ^a	Double-Blind Treatment									Safety Follow-Up Visit ^e
Visit	1	2	3	4	5	6	7	8			
Study week		0	2 ^b	4	6 ^b	8	10 ^b	12	UV ^c	Early D/C Visit ^d	16 (or 4 weeks after Early D/C)
Window in Days	-28 to -1	NA	±2	±2	±2	±2	±2	±2	NA	NA	±2
CSF collection (optional) ^t	x							x			
MRI ^u	x			x		x		x	(x)	(x)	
Concomitant medications	x	x		x		x		x	x	x	x
Adverse events	x	x		x		x		x	x	x	x
Study treatment dispensation		x		x		x		x ^v			
Study treatment compliance				x		x		x		x	

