- ^s Semi-structured telephone interviews will be conducted every 6 weeks (± 3 days) between study visits (when there are dates overlapping with site visits, telephone calls will not occur). Please see [Appendix 10](#) for more details. If the participant answers YES to any question during the semi-structured telephone interview, the answer should be discussed and reviewed by the investigator. If warranted, the participant should return for an UV. If an unplanned pregnancy is suspected, an UV to confirm the pregnancy is required.

Table 3 Schedule of Pharmacokinetic Samples for Double-Blind Treatment

Visit	Timepoint	Sample Type
Day 1 (Week 0) and 29 (Week 4)	Prior to the morning dose, fasted ^a	PK (plasma)
	1–2 hours after dosing, fasted	PK (plasma)
Day 1 (Week 0) and Day 29 (Week 4) (if applicable) ^b	Prior to the morning dose, fasted ^a	PK (plasma)
	1 hour (\pm 10 minutes) after dosing, fasted	PK (plasma)
	2 hours (\pm 10 minutes) after dosing, fasted	PK (plasma)
	4, 6, and 8 hours (\pm 10 minutes) after dosing ^c	PK (plasma)
Day 57 (Week 8)	Predose ^a	PK (plasma)
Day 85 (Week 12)	Predose ^a	PK (plasma)
Unscheduled visit ^d	NA	PK (plasma)
Early D/C visit	NA	PK (plasma)

D/C = discontinuation; NA=not applicable; PK=pharmacokinetic; PPI=proton pump inhibitor.

Notes:

Morning clinic visits are preferred for all visits but are required on Days 1, 15, and 29. Prior to each morning clinic visit, participants should be instructed not to take their morning dose and to bring their study medication with them to their clinic visit. The dates and times of the most recent prior meal, last dose of oral study drug (prior to the clinic visit), and timing of oral study drug administration in the clinic should be recorded at each clinic visit. Use of PPIs, H₂-receptor antagonists, and/or other antacids (e.g., bismuth subsalicylate, calcium carbonate, aluminum-magnesium hydroxide) should be recorded as concomitant medications, including the date and time of last administration at each clinic visit.

Single-dose acid-reducing agents are not permitted on the day of an in-clinic visit with PK assessments.

- ^a Participants should be fasting for >6 hours overnight prior to the sample collection, which must be performed at the clinic in the morning. The PK samples should be collected 5–30 minutes prior to the fenebrutinib dose.
- ^b For participants participating in the intensive PK sample collection only.
- ^c Fasting is not required for these samples.

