Participants will be closely monitored for safety throughout the study. Participants should be assessed for toxicity prior to each dose; treatment will be administered only if the clinical assessment and local laboratory test values are acceptable. Urgent safety concerns should be discussed with the Sponsor immediately upon occurrence or awareness to determine if the participant should continue or discontinue study treatment.

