8.3 ADVERSE EVENTS, SERIOUS ADVERSE EVENTS, AND OTHER SAFETY REPORTING

The definitions of adverse event and serious adverse event can be found in [Appendix 3](#).

Adverse events will be reported by the participant (or, when appropriate, by a caregiver, surrogate, or the participant's legally authorized representative).

The investigator and any qualified designees are responsible for detecting, documenting, and recording events that meet the definition of an adverse event or serious adverse event and remain responsible for following up adverse events that are serious, are considered related to the study treatment or study procedures, or caused the participant to discontinue the study treatment (see Section [7](#)).

8.3.1 Time Period and Frequency for Collecting Adverse Event and Serious Adverse Event Information

After informed consent has been obtained but prior to initiation of study drug, only serious adverse events caused by a protocol-mandated intervention should be reported. The paper Clinical Trial Event/*Special Situations* Form provided to investigators should be completed and submitted to the Sponsor or its designee immediately (i.e., no more than 24 hours after learning of the event), either by faxing or by scanning and emailing the form using the fax number or email address provided to investigators. All other medical occurrences that begin before the start of study treatment but after obtaining informed consent will be recorded on the General Medical History and Baseline Conditions eCRF, not the Adverse Event eCRF.

All adverse events will be reported from the start of treatment until 28 days after the final dose of study treatment at the timepoints specified in the schedule of activities (see Section [1.3](#)).

All serious adverse events will be recorded and reported to the Sponsor or designee immediately and under no circumstance should this exceed 24 hours, as indicated in [Appendix 3](#). The investigator will submit any updated serious adverse event data to the Sponsor within 24 hours of it being available.

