Appendix 10 Telephone Interviews

The purpose of the semi-structured interview is to identify and collect information on any changes in the *participant's* health status that may warrant an unscheduled visit (e.g., new or worsening neurological symptoms, suspected unplanned pregnancy). The telephone interview will be conducted by treating team personnel familiar with the *participant(s)* (see [Table 2](#)).

The questions below will be asked and the *participant's* answers during the telephone interview will be recorded:

1. Since your last visit or telephone interview, have you had any new or worsening neurological symptoms (such as sudden changes in your thinking, alterations in your thinking, alterations in your behavior, visual disturbance, extremity weakness, limb coordination problems or gait abnormalities) that have persisted over more than one day?
2. Since your last visit or telephone interview, have you had any new or worsening medical problems?
3. How do you feel overall? Have you lost your appetite, are you nauseous, fatigued, have changes in your sleep patterns?
4. Since your last visit or telephone interview, have you had any infections or signs suggestive of infection, such as fever, headache, sore throat, cough, altered digestive transit, and/or burning sensation while urinating?
5. For female *participants*, since your last visit or telephone interview, have you had a positive urine pregnancy test?
6. Since your last visit or telephone interview, have you taken any new medicines (including medicines to treat multiple sclerosis, steroid medicines, or medicines that reduce the acid in your stomach)?

If the *participant* answered YES to any question, discuss and review the *participant's* answer(s) with the treating investigator. If warranted, the *participant* should return for an unscheduled visit. If an unplanned pregnancy is suspected, an unscheduled visit to confirm the pregnancy is required.

All relevant information should be recorded in the appropriate *electronic Case Report Form*.

Appendix 11

Investigational Medicinal Product and Non-Investigational Medicinal Product Designations (for Use in European Economic Area and United Kingdom)

Table 1 Investigational, Authorized Auxiliary, and Unauthorized Auxiliary Medicinal Product Designations for European Economic Area

Product Name	IMP/AxMP Designation	Marketing Authorization Status in EEA	Used within Marketing Authorization

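### Open-label extension, Weeks 0–12: scheduled visits collect adverse events and medicines 84 days apart, against 28 in the double-blind phase, although participants already attend at Weeks 4 and 8

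*Protocol*

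**What the plan says.** Protocol Section 1.3, Table 1 (double-blind phase) has a row for "Adverse events" and one for concomitant medications. On treatment, both are marked at Weeks 0, 4, 8 and 12.

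Table 2 (OLE) has the same two rows. Both are marked at baseline (which is the double-blind Week 12 visit), at Week 12 and at later visits, and also in the unscheduled, early-discontinuation and safety follow-up columns. Both are blank at Weeks 2, 4, 6, 8 and 10.

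Participants nevertheless have visits in those weeks. The row "Limited chemistry panel: ALT, AST, total and direct bilirubin testing" is marked at Weeks 2, 4, 6, 8 and 10. Immunoglobulins are marked at Weeks 4 and 8, and ECG and urinalysis at Week 4. Weeks 6 and 10 carry footnote b, which prefers a clinic visit but provides for the case "if these are performed by an accredited local laboratory". Weeks 4 and 8 do not carry that footnote.

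Telephone interviews are planned every 6 weeks, within 3 days either side. Table 2 footnote s adds that "when there are dates overlapping with site visits, telephone calls will not occur". Appendix 10 shows that the interview asks about both health and new medicines.

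Section 8.3.1 sets the reporting period and ties it to the visit schedule in Section 1.3: "All adverse events will be reported from the start of treatment until 28 days after the final dose of study treatment at the timepoints specified".

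**The concern.** For participants who had placebo in the double-blind phase, OLE Weeks 0–12 are the first 12 weeks on fenebrutinib. That is the period in which the double-blind schedule asked about events and medicines every four weeks. In the OLE the scheduled asking lapses for three times as long, although the same people are at the site at Weeks 4 and 8.

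Other non-hepatic checks do not fill the space. Hematology, vital signs, the suicidality scale and the relapse query are marked at Weeks 4 and 8 in Table 1, but are blank between baseline and Week 12 in Table 2. Appendix 6 lists infections, bleeding, cytopenias and gastrointestinal effects among the risks. Between the two marked visits, early non-serious forms of these would come to light mainly through spontaneous report, or through a Week 6 call that may not take place.

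Medicines matter too. Section 6.8.2.1 says that acid-reducing agents lower absorption of fenebrutinib, and Section 6.8.3 prohibits strong CYP3A inhibitors and strong or moderate inducers. A question at Week 4 could reveal a new prescription up to 12 − 4 = 8 weeks sooner than one at Week 12.

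**Working it through.** **Inputs.** Sample size 102, randomized 2:1, with 34 on placebo and 3% dropout assumed (Protocol Sections 4.1 and 9.2). Marks and windows from Tables 1 and 2: ±2 days for double-blind visits and for OLE visits up to Week 12, and ±3 days for calls.

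1. **Participants with first exposure.** 102 × 1/3 = 34, which reproduces the plan's figure. With 3% dropout, 34 × 0.97 ≈ 33. The documents give no OLE uptake, so 34 is an upper bound.

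2. **Double-blind interval.** Marks fall on days 0, 28, 56 and 84, so each gap is 4 × 7 = 28 days. With windows the first gap is 28 ± 2 = 26 to 30 days, and later gaps are 28 ± 4 = 24 to 32 days.

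3. **OLE interval between scheduled visits.** Marks fall on days 0 and 84, so the gap is 12 × 7 = 84 days (82 to 86 with the window). The ratio is 84 / 28 = 3.

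4. **If the Week 6 call takes place.** It falls on day 42 ± 3, that is days 39 to 45.
   - Baseline to call: 42 days (39 to 45).
   - Call to Week 12: 84 − 42 = 42 days. The shortest is 82 − 45 = 37 and the longest is 86 − 39 = 47.

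5. **Whether the call takes place.** The Week 6 visit window is 42 ± 2, or days 40 to 44. This lies wholly inside the call window of days 39 to 45. If the visit is held in clinic, which footnote b prefers, footnote s allows the call to be omitted, and neither row is marked at that visit. If the blood is drawn at a local laboratory instead, the call can go ahead.

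6. **With marks added at Weeks 4 and 8.** Marks fall on days 0, 28, 56 and 84, as in step 2. The longest nominal gap is 28 days, and at most 32 with windows. This holds with or without a Week 6 call.

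**The case against.** The strongest reply is that recording does not depend on a table mark. Section 8.3 states that "The investigator and any qualified designees are responsible for detecting, documenting, and recording events that meet the definition of an adverse event". Appendix 3 (A3-3.1 and A3-7) has the investigator record an event when it occurs, Section 8.3.2 prefers open-ended questioning, and Section 8 adds: "Participants will be closely monitored for safety throughout the study". A blank cell also does not prove that a topic goes unaddressed. Section 6.4 requires a tablet count at each clinic visit, including in the OLE, yet Table 2 marks compliance in Weeks 0–12 only at baseline and Week 12.

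The main identified risk is also closely followed. ALT and AST are tested every two weeks to Week 10. A value above 3 × ULN requires an unscheduled visit and questions about symptoms and co-medications. Section 2.3 reports that over 650 participants had already received this dose. Lighter scheduled questioning about mild events can therefore be defended as a design choice.

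Most of this stands, and it sets the low priority. It does not remove the point, because none of these provisions schedules a question at Weeks 4 and 8. The same general duties apply in the double-blind phase, where the sponsor still scheduled collection every 28 days.

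A reader might infer more than the documents support:

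- **That safety information is not collected for 12 weeks.** Both rows are marked at unscheduled and early-discontinuation visits, and serious events and events of special interest must be reported within 24 hours. Events from the whole interval remain reportable at Week 12.
- **That the Week 6 call would reach back only to Week 4.** One question does begin "Since your last visit or telephone interview, have you had any new or worsening medical problems", but another in Appendix 10 asks how the participant feels overall, with no look-back limit.
- **That footnote s must be rewritten.** The added marks give 28 days by themselves. A rule that forced the call could place it within days of an in-clinic Week 6 visit.

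**Conclusion.** The gap is real but small in consequence. Among scheduled OLE visits in Weeks 0–12, adverse events and concomitant medications are marked 84 days apart, against 28 in the double-blind phase. The gap is about 42 days if the Week 6 call is made. It matters most for up to 34 former placebo participants, about 33 at the plan's own dropout rate and fewer if some decline the OLE.

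The effect is limited to later elicitation, with possible recall or dating error, of non-serious, non-hepatic events and of new medicines. A late-discovered medicine has a limited consequence as well: under Section 7.1 only chronic need for a prohibited one requires stopping treatment, and other necessary use is discussed with the Medical Monitor.

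It would be wrong to infer a threat to the trial's results. The randomized comparison ends before the OLE begins. SAP Section 5.4.2.1 summarizes adverse events by term and highest grade, so no specified analysis changes. The documents do not show that any event would be lost.

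The conclusion rests on reading the two rows as marked in Table 2 and on the ±2-day window for visits up to Week 12. It is a cheap improvement of low priority.

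**What to change.** At the next amendment made for other reasons, mark adverse events and concomitant medications in Table 2 at the existing OLE Week 4 and Week 8 visits, as Table 1 does. Leave footnote s unchanged.

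This is 2 rows × 2 visits = 4 table marks and adds no visit and no call. The cost is a few minutes at each of the two visits and some extra case report form entries for mild events. Appendix A1-1 requires ethics committee and health authority approval for a substantial amendment, so the change should be bundled rather than submitted alone.
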